## Methods and Procedures Attachment

Individual subjects will report to the Bentson Bunker Fieldhouse, Room 14. They will be instructed to wear appropriate shorts or pants that can be rolled up to expose the gastrocnemius (calf) muscle. Upon their arrival to room 14, they will be given a copy of the consent form to read and sign. The subject will be given the opportunity to ask questions to the researchers regarding the consent form at this time. The subjects will lie prone on a treatment table for insertion of the thermocouple and for the ultrasound treatment. A towel will be placed under the subjects' knee as needed for comfort. The 21-gauge flexible, implantable thermocouples (very small temperature probes) will be calibrated before the study begins and then will be sterilized in MetriCide for at least 12 hours before use. The thermocouples will be inserted into the medial side of the gastrocnemius muscle horizontally and parallel to the ultrasound treatment surface at depths of 1.0cm, 1.75cm, and 2.5cm. Horizontal insertion of the thermocouples allows the ultrasound to be applied without interfering with the thermocouple lead wires.

The subject will lay prone on the treatment table with the foot and lower leg off of the treatment table in a relaxed, comfortable position. The following procedures will be completed using universal precautions:

1. The investigator will prep the treatment area by having the subject flex the calf to determine the proper location for the ultrasound treatment in the middle of the medial gastrocnemius muscle belly at its largest girth.
  - a. A carpenter's square with markings along the vertical arm at the three experimental depths (1.0, 1.75, 2.5 cm) will be used.

- b. The horizontal arm of the carpenter's square will be covered in tape. The carpenter's square is then placed just proximal to the treatment mark while the level on the horizontal arm is used to maintain a level measure.
- c. Marks will be made on the muscle belly parallel to the marks on the vertical axis at 1.0, 1.75 and 2.5 cm depths.
- d. A mark is also made on the horizontal arm tape in line with the treatment mark on the medial gastrocnemius.

- 2. The Terason uSmart 3300 diagnostic ultrasound unit will be used to measure the adipose thickness over the treatment area and look for abnormalities in the treatment and thermocouple insertion areas. Aquasonic® 100 ultrasound gel will be placed on the 15L4 transducer. The transducer with gel will be placed over the mark of the treatment area. Once the transducer is in place, the screen will be frozen and the skin and adipose thickness will be measured using the caliper tool.
  - a. If adipose thickness is greater than 1.0 cm or any tissue abnormalities exist that could contraindicate thermocouple insertion, the subject will be excluded.

3. The thermocouples will be removed from the MetriCide after sterilizing for a minimum of 12 hours prior to insertion.
  - a. The distal aspect of the thermocouple will be wiped dry with sterile gauze.
  - b. A mark with a sharpie will be made on each thermocouple just past the length marked on the horizontal arm of the carpenter's square. This allows the tip of each thermocouple to be directly below the treatment site. A second mark will be made at 5 cm to make sure the thermocouple does not go too deep into the tissue.

- c. The distal end of the thermocouple will be wiped clean again using a 70% isopropyl alcohol wipe up to the marks and then the thermocouple will be wrapped in sterile gauze until it is inserted.

[figure not shown]
4. The insertion areas will be shaved to remove any body hair (if necessary) and cleaned using Betadine.

a. Once the Betadine dries, 70% isopropyl alcohol will be wiped over the insertion area and given time to dry.

5. The subject will be instructed to take two deep breaths, while the researcher lightly grasps the gastrocnemius to confirm muscle relaxation.

a. During the second exhalation, the 1.16 in needle catheter will be placed into the subject's calf at the 1.0 cm depth insertion mark using the level to guide the needle in. The needle will be removed leaving the catheter in the tissue.

- 
- b. The thermocouple will be threaded through the catheter to the appropriate depth marked on the thermocouple and the catheter will be removed.

- 
- c. The thermocouple will be secured using medical tape to keep it from moving.
- d. This procedure will be performed 3 times, with one thermocouple placed at each respective depth: 1.0 cm, 1.75 cm, and 2.5 cm.
6. Each thermocouple will be attached to the Iso Thermex electronic thermometer (Columbus Instruments, Columbus, OH), which will measure and record intramuscular temperatures from the tips of the thermocouples.
7. An ultrasound treatment template will be applied at the treatment site and secured with tape to maintain consistent treatment size.
  - a. This template will be twice the size of the transducer's Effective Radiating Area (ERA).

8. A metronome will be utilized to consistently move the transducer at a rate of 4 cm/s .
9. The ultrasound treatment will begin once the intramuscular temperature has remained the same for a minute.
10. Each subject will receive one ultrasound treatment at the following parameters: 3 MHz frequency, 1.0 W/cm^2 intensity, and 100% duty cycle using the Chattanooga Intelect® Legend XT.
  - a. Termination of treatment will result when any of the following occur:
    - i. A 15-minute treatment time is obtained.
    - ii. A 4°C temperature increase occurs at all three depths as this has been shown as the necessary temperature change to increase tissue extensibility.
    - iii. A 45°C temperature is reached at any depth, due to concern of tissue damage at high temperatures.
    - iv. The subject experiences any pain or discomfort during the treatment.
11. Following the treatment, the ultrasound gel will be wiped from the leg, the template and thermocouples will be removed, and the insertion sites will be cleaned with 70% isopropyl alcohol wipes and covered with a band aid.
12. The subject will then be instructed on the possibility of minor soreness for the next day or two and instructed on an icing schedule to decrease discomfort.

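### No supplied step checks that the gastrocnemius reaches 2.5 cm below the skin, so the deepest reading cannot be shown to come from the muscle the protocol names

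*Protocol*

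**What the plan says.** The Methods and Procedures Attachment states the target tissue and the three depths together: the probes are "inserted into the medial side of the gastrocnemius muscle horizontally and parallel to the ultrasound treatment surface at depths of 1.0cm, 1.75cm, and 2.5cm". Depth is set from outside the leg. Step 1 says "A carpenter's square with markings along the vertical arm at the three experimental depths (1.0, 1.75, 2.5 cm) will be used", and the marks are transferred to the calf at the same distances for every subject. The natural reading is depth below the skin surface.

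The site is chosen by having the subject flex the calf, and is "in the middle of the medial gastrocnemius muscle belly at its largest girth".

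Step 2 uses diagnostic ultrasound to "measure the adipose thickness over the treatment area and look for abnormalities in the treatment and thermocouple insertion areas". For the measurement itself, "the screen will be frozen and the skin and adipose thickness will be measured using the caliper tool". The rule that follows is: "If adipose thickness is greater than 1.0 cm or any tissue abnormalities exist that could contraindicate thermocouple insertion, the subject will be excluded". The supplied text has no criterion for muscle thickness, no measurement of the deep border and no imaging of the tip after insertion.

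The SAP analyses 2.5 cm as one of three levels of depth in a 3×4 repeated measures ANOVA with 25 subjects. It has no rule for a tip that lies outside the intended muscle.

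**The concern.** Naming the gastrocnemius as the tissue measured at 2.5 cm assumes that the muscle extends that far below the skin in every subject. The scan looks at the layers above the muscle and stops there. The one thickness limit is an upper limit on fat. It removes the subjects in whom the least muscle is needed to reach 2.5 cm, and gives no protection at the lean end, where the most is needed.

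Depth is the study's main comparison. If the deepest tip is within the gastrocnemius in some subjects and at or beyond its deep border in others, the 2.5 cm results mix locations in a way that depends on body build. The contrast between depths could then be partly a contrast between tissues. Nothing recorded under the present procedure would let anyone separate the two afterwards.

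**Working it through.** The plan gives no muscle thickness, effect size or basis for the sample size, so there is no figure of its own to reproduce. The check is geometric, followed by a range under stated assumptions.

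**Inputs from the documents**
- Deepest probe: 2.5 cm, taken as depth below the skin (Protocol, opening paragraph and step 1).
- Adipose above 1.0 cm is excluded, with no lower limit (Protocol, step 2).
- Sample size: 25 (SAP).

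**Step 1: muscle thickness needed.** Required thickness = 2.5 − (skin + adipose).

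| Skin + adipose (cm) | Required gastrocnemius thickness (cm) |
|---|---|
| 0.3 | 2.5 − 0.3 = 2.2 |
| 0.5 | 2.5 − 0.5 = 2.0 |
| 0.7 | 2.5 − 0.7 = 1.8 |
| 1.0 | 2.5 − 1.0 = 1.5 |

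The requirement rises as the subject gets leaner. This step uses only the protocol's depths and the reading of depth as distance from the skin.

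**Step 2: share of subjects with the tip past the deep border.** This needs a thickness distribution that the documents do not supply. Assume a normal distribution with SD 0.3 cm and vary the mean widely. Share = Φ((required − mean) / 0.3). At 0.5 cm skin + adipose, required = 2.0 cm:

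| Assumed mean (cm) | Calculation | Share past the border |
|---|---|---|
| 1.8 | Φ(0.2/0.3) = Φ(0.67) | about 75% |
| 2.0 | Φ(0) | 50% |
| 2.2 | Φ(−0.2/0.3) = Φ(−0.67) | about 25% |
| 2.5 | Φ(−0.5/0.3) = Φ(−1.67) | about 5% |
| 2.8 | Φ(−0.8/0.3) = Φ(−2.67) | about 0.4% |

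At 1.0 cm skin + adipose, required = 1.5 cm. Means of 1.8, 2.0 and 2.2 cm then give Φ(−1.00) = 16%, Φ(−1.67) = 5% and Φ(−2.33) = 1%.

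The answer runs from negligible to most of the sample, depending on an input nobody has recorded.

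**Step 3: would a low share matter in 25 subjects?** For an assumed share p, the expected number is 25p and the chance of at least one is 1 − (1 − p)^25.

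| Assumed p | Expected number | Chance of at least one |
|---|---|---|
| 2% | 0.5 | 40% |
| 5% | 1.25 | 72% |
| 10% | 2.5 | 93% |
| 20% | 5 | 99.6% |

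So even a modest share would probably put at least one affected subject in the sample.

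**Step 4: does any other step verify placement?** Of the thermocouple, step 3 says "A second mark will be made at 5 cm to make sure the thermocouple does not go too deep into the tissue". Insertion is horizontal, so that mark limits the length inserted and not the vertical position. The abnormality check in step 2 concerns contraindications to insertion; a normal but thin muscle would pass it.

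**The case against.** The strongest reply is that the problem may hardly ever occur. The site is the belly at its largest girth, a sensible choice that favours thick muscle, and the operator is already imaging the area. With a mean thickness of 2.5 cm or more, the table above gives 5% or less. This stands: the documents cannot show that the problem is common, and siting is a real, though unverified, safeguard.

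The second reply is that a tip past the gastrocnemius may lie in another calf muscle. The SAP's title speaks of intramuscular heating rates and its ANOVA factor is depth in centimetres; neither names the gastrocnemius. A reading from underlying muscle would still fit the SAP's wording. This also stands. What fails in that case is the protocol's naming of the gastrocnemius.

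Three stronger readings are tempting, and the documents support none of them.
- A reader might infer that a quarter to three quarters of the 2.5 cm readings are misplaced. Those shares come from assumed means placed around the 2.0 cm requirement; thicker assumed means bring them close to zero.
- A reader might infer that the 2.5 cm heating rate is biased. Nothing in the documents says that adjacent muscle, or tissue near the fascial border, heats differently at the same depth.
- A reader might infer that the protocol as a whole has no such check. Some pages were removed and a figure is missing, so the statement can only be that no supplied step contains one.

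The shallow end raises a separate question, since the 1.0 cm adipose limit equals the shallowest probe depth. That does not answer the point about the deepest tip.

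**Conclusion.** The concern holds as a gap in verification. The protocol asserts gastrocnemius placement at 2.5 cm, and no supplied step confirms it. The required thickness of 2.2 cm down to 1.5 cm, for skin plus adipose of 0.3 to 1.0 cm, follows from the protocol's depths if depth is measured from the skin, as the external square implies.

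The frequency of failure is unknown. The range of about 75% down to 0.4% at 0.5 cm skin plus adipose shows how far the answer depends on the assumed mean, with SD 0.3 cm also assumed; it is not an estimate for this population. The effect on heating rate is not established.

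This is a cheap, worthwhile improvement. It does not invalidate the design. It is worth making before data collection, because the measurement has to be taken at the visit, and it decides whether the 2.5 cm result can be described as gastrocnemius heating.

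**What to change.** At the step 2 scan, set the imaging depth to include the deep border of the medial gastrocnemius, and record the depth of that border from the skin alongside the skin and adipose reading. Flag any subject whose border is shallower than 2.5 cm. Flagging need not mean exclusion.

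In the SAP, state in advance that the 2.5 cm heating rate and the depth comparison will be reported with and without flagged subjects. For the ANOVA, leave a flagged subject out at all three depths, so that the depths are compared in the same people. If flagged readings stay in the main result, describe it as heating 2.5 cm below the skin and not as gastrocnemius heating at 2.5 cm.

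The cost is one more caliper reading at a scan already planned and one sensitivity analysis, with no additional subjects. The restricted analysis may rest on fewer than 25 subjects. The flag also tests the nominal depth only; it does not image the tip, so error in the external square remains.

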Intramuscular Heating Rates of a Chattanooga Intelect XT Therapeutic Ultrasound with a 3 MHz frequency and 1.0 W/cm² Intensity at Three Depths up to 2.5 cm.

1-22-19

Statistical Analysis Plan:

Twenty-five subjects will be recruited from the Institution's student population using the University email Listserv. Descriptive statistics will be utilized to determine the rate of increase for each depth. A 3×4 repeated measures ANOVA will be used to determine differences in temperature increases at 3 depths (1.0, 1.75 and 2.5 cm) at 4 different time points (baseline, 5,10,15 minutes). The level of significance will be set at $p \leq .05$

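### The 1.0 cm adipose limit equals the shallowest probe depth and leaves open whether skin counts, so an eligible subject's 1.0 cm tip could lie in fat or at the fat-muscle boundary

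*Protocol*

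**What the plan says.** All protocol steps cited are in the Methods and Procedures Attachment.

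- **Depth marks (step 1.c).** These are made with an external carpenter's square before any scan: "Marks will be made on the muscle belly parallel to the marks on the vertical axis at 1.0, 1.75 and 2.5 cm depths".
- **Scan (step 2).** The opening sentence says the diagnostic unit "will be used to measure the adipose thickness over the treatment area". The later operating sentence says "the skin and adipose thickness will be measured using the caliper tool".
- **Exclusion (step 2.a).** The thickness condition is "If adipose thickness is greater than 1.0 cm". Skin is not mentioned, and a value of exactly 1.0 cm passes.
- **Insertion (steps 3.b and 5.a).** The length mark on each probe is meant to bring its tip under the treated area: "This allows the tip of each thermocouple to be directly below the treatment site". The first catheter goes in "at the 1.0 cm depth insertion mark using the level to guide the needle in". No step between the scan and insertion adjusts the marks for the measured thickness.
- **Recording (step 6).** The probes connect to a thermometer "which will measure and record intramuscular temperatures from the tips of the thermocouples".
- **Analysis (SAP).** "Descriptive statistics will be utilized to determine the rate of increase for each depth". The same data enter a 3×4 repeated measures ANOVA of depth by time, and the planned number of subjects is 25.

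**The concern.** The study is about muscle heating at three depths, and the thickness limit is the only written step that keeps overlying fat away from the shallowest probe. That limit equals the probe depth, so there is no margin. If it applies to adipose alone, the skin comes on top and muscle can begin deeper than 1.0 cm in an eligible subject.

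A fat or boundary reading would then enter one level of the depth factor only. The 1.0 cm heating rate, and its contrast with 1.75 and 2.5 cm, could partly reflect tissue type as well as depth. No described step images the tip after insertion, and thickness is not listed as a reported variable, so a reader could not tell whether this had happened.

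**Working it through.** **Inputs from the documents:** probe depths of 1.0, 1.75 and 2.5 cm; exclusion only above 1.0 cm; 25 subjects.

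**Assumptions, because the documents give no values:** skin thickness s = 0.1 to 0.3 cm; difference d = 0.5 to 2 °C between the temperature rise recorded at an affected tip and the rise in muscle at the same depth.

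**Where depth starts.** The text does not say. The marks come from an external square, are made before the scan and are not changed afterwards. A depth below the muscle surface could not be marked in that way without knowing the overlying thickness. Depth from the skin is therefore the natural inference, and the rest of the check uses it.

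**Geometry.** With adipose thickness a, muscle begins at depth s + a. A tip at depth D is in muscle only if s + a < D.

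*Interpretation A: the limit applies to adipose alone (a ≤ 1.0 cm).* The 1.0 cm tip is in fat or at the boundary when s + a ≥ 1.0, that is, for a from 1.0 − s to 1.0 cm. The deepest eligible muscle surface is 1.0 + s, so the tip lies at most s above muscle. The least muscle over the 1.75 cm tip is 1.75 − (1.0 + s) = 0.75 − s.

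| Assumed s (cm) | Adipose range affected (cm) | Deepest muscle surface (cm) | Tip above muscle, at most (cm) | Muscle over 1.75 cm tip, at least (cm) |
|---|---|---|---|---|
| 0.1 | 0.9 to 1.0 | 1.1 | 0.1 | 0.65 |
| 0.2 | 0.8 to 1.0 | 1.2 | 0.2 | 0.55 |
| 0.3 | 0.7 to 1.0 | 1.3 | 0.3 | 0.45 |

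The 1.75 cm tip would be in fat only if s exceeded 0.75 cm. Only the shallowest level is exposed.

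*Interpretation B: the limit applies to skin plus adipose (s + a ≤ 1.0 cm).* An exactly placed 1.0 cm tip is at worst on the boundary, and only when the total is exactly 1.0 cm. Placement error alone could put it in fat. The 1.75 cm tip has at least 1.75 − 1.0 = 0.75 cm of muscle above it.

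**Effect on the 1.0 cm mean.** One affected subject among 25 shifts the mean rise by d/25, or 4% of d:

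- d = 0.5 °C: 0.5/25 = 0.02 °C
- d = 1 °C: 1/25 = 0.04 °C
- d = 2 °C: 2/25 = 0.08 °C

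The contrast between 1.0 and 1.75 cm moves by the same amount, because the 1.75 cm value is unaffected. The direction and the number of such subjects cannot be derived.

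**The case against.** The strongest reply is that step 2.a follows directly on the caliper sentence, which names skin and adipose together, so an investigator would apply the limit to that measurement. The problem then shrinks to a single value and is mainly one of wording. That interpretation is plausible, but the step's opening sentence and 2.a itself name adipose only, so the text supports either.

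Other points on the same side:

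- **The zero point is inferred.** If depth were measured from the muscle surface, the problem would disappear. This stands as a limit. The marking procedure makes it unlikely, and the protocol would still need to say so. A figure near step 3 is not visible in the text available, so some caution is due.
- **No size is shown.** Correct. The values of s and d are assumptions, nobody may be affected, and nothing shows that a conclusion about depth would change.
- **A constant offset cancels.** The SAP analyses temperature increases with baseline as a time point, so a fixed temperature difference between fat and muscle drops out. Only a different heating response matters. This is right, and it is why d is defined above as a difference in rise. It qualifies the illustration and leaves the geometry unchanged.
- **A limit just below 1.0 cm still admits 0.99 cm.** True: that leaves 0.01 cm of margin with level-guided placement. The change removes the window that the rule itself creates, but not placement error.

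**Conclusion.** The concern holds as a bounded, inexpensive improvement. It is not a demonstrated bias. The limit equals the shallowest probe depth, and the protocol does not say whether skin is included. Under the literal wording, with depth taken from the skin, the rule admits subjects whose 1.0 cm reading would not come from within muscle. Under the other interpretation, only exact equality is at issue. What rests on the documents is the equality of the two figures, the unsettled wording and the absence of any later adjustment of the marks. What rests on inference or assumption is the skin as zero point, the width of the affected range and the °C figures. Confidence is medium.

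**What to change.** In the protocol:

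1. Reword step 2.a so that skin plus adipose thickness must be less than 1.0 cm, that is, below the shallowest probe depth. Use the caliper measurement already taken, or the sum if skin and adipose are recorded separately.
2. State that probe depth is measured from the skin surface.
3. Report each subject's thickness, so that readers can see how close the 1.0 cm tip lay to the boundary.

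Under the adipose-only interpretation this closes the whole range in the table. Under the other it removes exact equality and settles the wording.

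The cost is two sentences and one reported variable, with no new measurement and no change to the SAP. The downside is possibly a few more volunteers screened out: under the adipose-only interpretation, those with skin plus adipose of 1.0 cm or more. The documents do not allow that number to be estimated.

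### Does marking all three thermocouples with one common length confound depth with lateral position under the transducer?

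*Protocol*

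**What the plan says.** All of the placement instructions are in the Protocol's Methods and Procedures Attachment.

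- Step 1.c sets the three entry points on the side of the calf: "Marks will be made on the muscle belly parallel to the marks on the vertical axis", at 1.0, 1.75 and 2.5 cm.
- Step 1.d takes a single horizontal length: "A mark is also made on the horizontal arm tape in line with the treatment mark on the medial gastrocnemius".
- Step 3.b transfers it to every probe: "A mark with a sharpie will be made on each thermocouple just past the length marked on the horizontal arm". The stated purpose is that "This allows the tip of each thermocouple to be directly below the treatment site". It then adds a limit: "A second mark will be made at 5 cm to make sure the thermocouple does not go too deep into the tissue".
- Step 5.a inserts the needle "using the level to guide the needle in". Step 1.b places that level on the square's horizontal arm.
- Step 5.b says "The thermocouple will be threaded through the catheter to the appropriate depth marked on the thermocouple". It does not say whether the mark is read at the skin, at the catheter or at the square.
- Step 7 puts a template of twice the effective radiating area (ERA) at the treatment site. The ERA value is not given.

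The SAP makes depth a factor of the main analysis: a 3×4 "repeated measures ANOVA will be used to determine differences in temperature increases at 3 depths". It also describes the heating rate at each depth. The planned sample is 25.

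**The concern.** There is one length but there are three entry points. With the subject prone, the side of the calf normally slopes outward from the 1.0 cm mark to the 2.5 cm mark, so the deepest probe has furthest to travel to reach the line below the treatment mark. If each probe is pushed in by the same amount measured from the skin, the 1.0 cm tip ends further across than the 2.5 cm tip.

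On such a flank that order is the same in every subject. Recruiting 25 subjects would not average it out, and a within-subject comparison of depths would not remove it. A difference in heating between depths could then be partly a difference in how central each tip was. No step records inserted lengths or checks tip position, so it could not be corrected afterwards. Depth is the factor under study, so this deserved a check.

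**Working it through.** The documents state no figure for tip position, so there is none to reproduce. The check is geometric.

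**Inputs from the Protocol.** Depths of 1.0, 1.75 and 2.5 cm; one common length L from the vertical arm to the treatment mark; horizontal insertion; a second mark at 5 cm; a template of 2 × ERA.

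**Inputs assumed.** Calf contour and ERA are not in the documents. Ranges are used below, with the treatment mark at the top of the contour.

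**1. Mark read at the vertical arm.** Let h(d) be the horizontal path from the skin to the treatment line at depth d. The gap between arm and skin is g(d) = L − h(d). The inserted length is L − g(d) = h(d), so each tip is on the line and the spread is 0 for any contour. Marking slightly beyond L shifts all three tips by the same amount.

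**2. Mark read at the skin.** Each tip overshoots by L − h(d). The spread between the 1.0 and 2.5 cm tips is h(2.5) − h(1.0), whatever L is. For a mean skin slope θ from the horizontal it equals 1.5 × cot θ: 1.50 cm at 45°, 0.87 cm at 60°, 0.40 cm at 75° and 0 at 90°.

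For a circular contour of radius R, h(d) = √(2Rd − d²):

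| R (cm, assumed) | h at 1.0 / 1.75 / 2.5 cm | Spread (cm) |
|---|---|---|
| 3 | 2.24 / 2.73 / 2.96 | 0.72 |
| 4 | 2.65 / 3.31 / 3.71 | 1.06 |
| 5.5 | 3.16 / 4.02 / 4.61 | 1.45 |
| 7 | 3.61 / 4.63 / 5.36 | 1.76 |

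Superellipse contours have half-axis a and exponent n, with n = 2 circular and n = 4 flat-sided. Here h(d) = a(1 − ((a − d)/a)^n)^(1/n), with a solved from a circumference C of 30 to 45 cm. The spreads run from 0.40 cm (C = 30, n = 4) to 1.79 cm (C = 45, n = 2).

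**3. Are the tips still under the template?** A circular template of area 2 × ERA has radius √(2·ERA/π): 1.13 cm for an ERA of 2 cm², 1.60 for 4, 1.78 for 5 and 2.52 for 10. If the arm touches the calf at the 2.5 cm mark, the 1.0 cm tip is off centre by the spread in the table, 0.72 to 1.76 cm. All of these fall inside the template at an ERA of 5 cm². At 2 cm², R = 3 and 4 do, but R = 5.5 and 7 do not. If the arm touches at the widest point, the shallow tip at R = 5 is 5 − 3.00 = 2.00 cm off, which is outside the 1.78 cm radius and inside 2.52. The tips can all lie under the template on the skin reading, but need not.

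**4. Is the error ordered by depth in the way that matters?** If heating falls off from the centre of the template (assumed), distance from centre counts, not signed position. Take the inserted length as the smaller of a and 5 cm, read at the skin:

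| Contour (assumed) | Distance from centre at 1.0 / 1.75 / 2.5 cm depth (cm) |
|---|---|
| C = 30, n = 2 | 1.85 / 1.08 / 0.58 |
| C = 45, n = 2 | 1.35 / 0.31 / 0.44 |
| C = 45, n = 4 | 0.37 / 0.91 / 1.18 |

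The shallow tip is furthest out in the first two contours and nearest in the third. The reversal arises because the 5 cm limit binds in the larger calf. In calves too small for it to bind, the shallow tip is the furthest out.

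**5. Which reading does the text support?** For the arm: L is measured from it, the stated purpose holds only there, and the level that guides the needle sits on the square. For the skin: the 5 cm mark limits travel in tissue. That second mark has its own purpose and does not fix where the first is read. The text does not decide between them.

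**The case for a change.** The strongest case for acting is that the skin is the ordinary place to read an insertion mark. The 5 cm mark is about tissue, step 3.c cleans the probe up to the marks as if that is the part that goes in, and no step says to put the square back after scanning, shaving and disinfection. The level in step 5.a guides the needle, not the length of thermocouple threaded. A lateral difference within the template is still a difference in position. A sentence on the reading point, or three gap readings against a square already in use, would cost about a minute per subject.

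Some of this stands. The reading point is not stated in the text available. On the skin reading with a sloping flank, the signed offset is ordered by depth. Under the assumed contours, the 2.5 cm probe would also need 5.1 to 6.2 cm at circumferences of 40 to 45 cm, beyond the 5 cm mark, so that mark and the stated aim of centring can pull apart in larger calves.

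It does not establish an error. The skin reading makes step 3.b contradict its own stated purpose, while the arm reading makes it correct. A figure belonging to these steps is not shown and may settle the matter, and what is lost with a figure cannot be counted as absent from the plan. A low cost does not turn an unconfirmed reading into a fault.

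**Conclusion.** The concern does not call for a change. The gap is one of detail: where a mark derived from the square is read at insertion. An investigator who has just measured L from the vertical arm, in order to bring each tip below the treatment mark, has an obvious way to use it, and used that way it gives zero spread.

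On the other reading the tips would be 0.4 to 1.8 cm apart sideways, but that range rests wholly on assumed contours and falls to zero on a vertical flank. Which tip is furthest from centre depends on the calf and on the 5 cm limit, and the tips may or may not leave the template depending on an ERA that is not given. Neither the direction nor the size of any temperature bias can be calculated from the documents, so no distortion of the ANOVA or of the heating rates has been shown. The SAP needs nothing on this point, because its analysis takes the recorded temperatures at the three nominal depths whichever way the mark is read. The conclusion would need another look only if the missing figure, or the investigator, confirmed that the mark is read at the skin.

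### Stopping at +4 °C can bias the later mean increases low, and the SAP prespecifies neither the time to +4 °C nor the share of subjects reaching it

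*Protocol*

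**What the plan says.** Step 10a of the protocol's Methods and Procedures Attachment lists four reasons to end treatment:

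- the time limit: "A 15-minute treatment time is obtained";
- a 4 °C "temperature increase occurs at all three depths as this has been shown as the necessary temperature change to increase tissue extensibility";
- a 45 °C "temperature is reached at any depth, due to concern of tissue damage at high temperatures";
- symptoms: "The subject experiences any pain or discomfort during the treatment".

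Step 6 connects each thermocouple to an electronic thermometer, "which will measure and record intramuscular temperatures from the tips of the thermocouples". No logging interval is given. Step 11 has the thermocouples taken out after treatment.

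The SAP sets the sample at twenty-five subjects and plans two analyses. The first is descriptive: "Descriptive statistics will be utilized to determine the rate of increase for each depth". How the rate is calculated is not defined. The second is inferential: "A 3×4 repeated measures ANOVA will be used to determine differences in temperature increases", over three depths and four times (baseline, 5, 10 and 15 minutes). Neither document mentions the time to +4 °C, the number of subjects reaching it, or the handling of subjects whose treatment ends before 15 minutes.

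**The concern.** The second stopping rule acts on the variable being analysed. A subject stopped by it has reached +4 °C at every depth, so all three times to +4 °C have been observed. What is lost is that subject's increase at any later grid time, which the ANOVA needs. The loss is informative, because good heating causes it.

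The subjects who remain at 15 minutes are those in whom at least one depth stayed below +4 °C. For the slowest depth, the 15-minute mean among them is held near or below 4 °C however well the device heats. Such a mean could be read as showing that the depth does not reach a useful temperature, when most subjects had reached it and left. If the ANOVA is run on complete cases, which the SAP neither says nor excludes, the early stoppers also drop out of the 5- and 10-minute means.

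The time to +4 °C and the share of subjects reaching it do not suffer from this stop. They also concern the only temperature rise to which the protocol attaches a functional benefit. The SAP includes neither.

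**Working it through.** The documents contain no derived figure to reproduce: the sample size comes without power, effect size or SD. The check is a comparison of the two documents, followed by illustrations.

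**1. What each stop does to the data**

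| Reason for stopping | Time to +4 °C at a given depth | Later grid increases |
|---|---|---|
| +4 °C at all three depths | observed at every depth | missing if before 15 min |
| 15 min reached | observed, or censored at 15 min | complete |
| 45 °C or discomfort | observed, or prevented by the stop | missing if before 15 min |

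**2. Size of the bias at the slowest depth**

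From the documents: target 4 °C, limit 15 min, n = 25. Assumed: linear heating, subject rates at the slowest depth normal with mean m and SD s = CV × m, and no other early stops.

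The rate needed to reach target by 15 min is c = 4/15 = 0.267 °C/min. With z = (c − m)/s, the share still treated at 15 min is Φ(z). Their mean increase is 15 × [m − s·φ(z)/Φ(z)]. Without stopping, the mean is 15m.

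| m (°C/min) | CV | s | z | Reached +4 °C | Left of 25 | Mean at 15 min, still treated | Mean without stopping |
|---|---|---|---|---|---|---|---|
| 0.30 | 20% | 0.06 | −0.556 | 71% | 7.2 | 3.4 °C | 4.5 °C |
| 0.30 | 40% | 0.12 | −0.278 | 61% | 9.8 | 2.7 °C | 4.5 °C |
| 0.40 | 20% | 0.08 | −1.667 | 95% | 1.2 | 3.5 °C | 6.0 °C |
| 0.40 | 40% | 0.16 | −0.833 | 80% | 5.1 | 2.7 °C | 6.0 °C |

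First row in full: φ(z)/Φ(z) = 0.342/0.289 = 1.18; 0.30 − 0.06 × 1.18 = 0.229; 15 × 0.229 = 3.4 °C.

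Two different heating rates thus give almost the same observed 15-minute mean. The share reaching target (61% to 71% against 80% to 95%) still separates them.

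**3. What the planned rate supplies**

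Under linear heating, time to target is 4/rate: 4/0.30 = 13.3 min and 4/0.40 = 10.0 min. If heating flattens, this misstates the time. Take an assumed curve ΔT = A(1 − exp(−t/τ)) with a 5 °C rise at 15 min, so A = 5/(1 − exp(−15/τ)). The mean rate is 5/15 = 0.333 °C/min and 4/rate = 12.0 min. The time on the curve is −τ·ln(1 − 4/A):

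- τ = 5 min: A = 5.26, time 7.1 min
- τ = 10 min: A = 6.44, time 9.7 min
- τ = 20 min: A = 9.48, time 11.0 min

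Nor does a mean rate fix the share reaching target: at 0.30 °C/min it moves from 71% to 61% as the CV goes from 20% to 40%.

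**4. Precision of a proportion with 25 subjects**

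For a hypothetical 20/25 = 80%, the Wilson 95% CI is 61% to 91% and the exact interval 59% to 93%. For 13/25 = 52%, the exact interval is 31% to 72%.

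**The case against.** The strongest reply is that the plan already addresses its stated subject. The SAP title concerns heating rates, and a rate per depth is planned. It gives an approximate average time to target, the means at 5, 10 and 15 minutes bracket that time, and the recorded temperatures would allow a direct calculation. This stands. A reader might infer that the trial cannot say how long each depth takes to warm by 4 °C; the documents do not support that. The gap is in what is prespecified, not in what is recorded.

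Second, +4 °C is one of four reasons to stop, with a rationale, and not a named endpoint. This also stands. A reader might treat it as the trial's own success criterion, but neither document states such an objective. The case for the addition rests on the conflict between the stopping rule and the analysis, not on a broken promise.

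Third, the rule needs all three depths, so the slowest decides. If that depth rarely rises 4 °C within 15 minutes, the rule removes little or nothing. This is correct, and it makes the bias conditional. It does not make the plan safe, since nothing in the documents indicates that the rule will seldom apply.

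Fourth, simple Kaplan-Meier medians would be the wrong tool, because a stop for 45 °C or discomfort before +4 °C is a competing event. This is right, and the fix takes account of it.

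**Conclusion.** The point holds in a limited form. The SAP does not prespecify the time to +4 °C or the proportion reaching it, and its ANOVA relies on later values that the +4 °C rule can remove selectively. Where the rule ends treatment before 15 minutes, the later means are biased low, most strongly at the slowest depth. In the illustration the shortfall at 15 minutes is about 1.1 to 1.8 °C at 0.30 °C/min (4.5 − 3.4 to 4.5 − 2.7) and 2.5 to 3.3 °C at 0.40 °C/min (6.0 − 3.5 to 6.0 − 2.7).

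These sizes rest on assumed rates, CVs, linearity and normality, none of which the documents give. How often the rule will apply is unknown. The direction of the bias does not depend on those figures; it needs only that some subjects stop under this rule before 15 minutes. The change should be made, because following the plan as written can give a truncated answer and the remedy is cheap.

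**What to change.** Add to the SAP, for each depth:

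- (a) the proportion of all treated subjects reaching +4 °C by 15 minutes, with a 95% CI (Wilson or exact);
- (b) the cumulative incidence of reaching +4 °C over time (Aalen-Johansen), with the median time where the curve reaches 50%. Censor administratively at 15 minutes, and count a stop for 45 °C or discomfort before +4 °C at that depth as a competing event.

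Compare the proportions between depths within subject by Cochran's Q, followed by paired McNemar tests. State the temperature logging interval, since it sets the precision of the times.

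The cost is some SAP text and one extra table, from temperatures the protocol already has recorded. Precision will be limited with 25 subjects, as the intervals above show. No stopping rule or other clinical procedure changes.
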